2 DESCRIPTION OF LONG-TERM EXTENSION (LTE) OBJECTIVES AND ENDPOINTS

2.1 Primary LTE Objective and Endpoint

The primary objective for the long-term extension (LTE) period is to evaluate the long-term safety and tolerability of BIIB092 in participants with MCI due to AD or with mild AD.

The primary safety endpoint that relates to this objective is the incidence of AEs and SAEs over the placebo-controlled period and LTE period of the study.

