
To assess the effect of BIIB092 on biomarkers in blood
	
Changes from Baseline over time up to Week 76 on blood levels of disease-related biomarkers, including but not limited to, tau and other markers of neurodegenerative disease

[REDACTED]
	
[REDACTED]

[REDACTED]
	
[REDACTED]

To assess the effect of BIIB092 on brain structure
	
Changes from Baseline over time up to Week 78 on MRI morphometric measures, including volume and cortical thickness of certain brain areas

CONFIDENTIAL

The information contained herein may not be used, disclosed, or published without the written consent of Biogen MA Inc.

Long-Term Extension Period Objectives and Endpoints	
Primary Objective	Primary Endpoint
To evaluate the long-term safety and tolerability of BIIB092 in participants with MCI due to AD or with mild AD	Incidence of AEs and SAEs over the placebo-controlled period and long-term extension (LTE) period of the study
Exploratory Objectives	Exploratory Endpoints
To further evaluate the immunogenicity of BIIB092 after multiple doses in participants with MCI due to AD or with mild AD	Incidence of anti-BIIB092 antibodies in serum over time up to Week 238
To further assess the effect of BIIB092 on disease progression as measured by fluid and radiological biomarkers, as well as additional clinical and health outcomes	
 • Changes over the placebo-controlled period and LTE period on the CDR-SB, MMSE, ISLT, Category Fluency and Letter Fluency tests from the DKEFS, DSST, Trails A, eCog, ADCS-ADL, FAQ, ADAS-Cog 13 (13-item), and NPI-10 • Changes over the placebo-controlled period and LTE period on the ZBI, QoL-AD, and RUD-Lite • [REDACTED] • Changes over the placebo-controlled period and LTE period on [REDACTED] MRI brain morphometric measures
To assess BIIB092 PK in serum [REDACTED] in participants with MCI due to AD or with mild AD	
 • Trough serum BIIB092 concentrations from serum samples collected at the visits indicated in the Schedule of Activities • [REDACTED]

CONFIDENTIAL

The information contained herein may not be used, disclosed, or published without the written consent of Biogen MA Inc.

This clinical study will collect samples that, under separate optional consent, may be used for future scientific and genetic research. Specific objectives related to this future research have not been determined.

CONFIDENTIAL

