3.2 Analyses Period

Depending on the purpose, different analyses will be conducted on the following study periods:

1. LTE period. Only data in the LTE period will be included in these analyses. This LTE analysis period will be applied to all the AE analyses, and the analyses will include all subjects who were dosed in the LTE period.
2. Placebo-controlled and LTE period. All the data in the placebo-controlled and LTE periods will be included in these analyses. This analysis period will be applied to analyses including, but not limited to all efficacy analyses and listings. The analyses will include all subjects who were dosed in the study including those who did not enroll into the LTE period. For example, line plot of CDR sum of box mean change from baseline over time. in the placebo-controlled and LTE period.
3. Placebo-controlled and LTE active treatment period. Active treatment period is defined as the study period(s) that a subject received BIIB092. For early start subjects – subjects who received BIIB092 in both placebo-controlled and LTE period, all the data (placebo-controlled and LTE periods) will be included in the analyses. For late start subjects – subjects who received placebo in the Placebo-controlled period and BIIB092 in the LTE period, only data in the LTE period will be included. This analysis period will be applied to majority of safety tables, and the analyses will include all subjects who were dosed in the study except for subjects who received only placebo in the placebo-controlled period and did not get dosed in the LTE period. An example is the incidence rate of adverse events in the placebo-controlled and LTE active treatment period.

Subjects to be included in a certain output is determined by both the analysis set and the analysis period. For example, the incidence table of adverse events in the LTE period will include subjects in the safety population for the LTE period, i.e., all randomized subjects who received at least one dose of study treatment in the LTE period. The incidence rate table of adverse events in the placebo-controlled and LTE active treatment period will include subjects in the safety population for the active treatment period, i.e., all randomized subjects who received at least one dose of study treatment in the active treatment period. In this SAP we do not separately define the analysis set in each analysis period.

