Only TEAEs will be included in the tables, unless otherwise specified. All SAEs (including pre-dosing SAEs) will be included in the listing of SAEs, with an indicator of pre-dosing or treatment-emergent. Only TEAEs will be included in other AE listings, if not otherwise specified. A listing of AE will be provided for the combined placebo-controlled and LTE period.

Pre-treatment AE: AE starting before LTE first dose are considered pre-treatment AE for LTE period if it does not qualify for above TEAE definition i.e., no worsening.

Analysis period and analysis displays

Analysis period will be specified for each output. However, for either analysis period in this SAP (LTE period or placebo-controlled and LTE active treatment period), AE data will be summarized by LTE treatment group (5 LTE treatment groups as low-dose BIIB092 125mg/4weeks, low-dose BIIB092 375mg/12weeks, medium-dose, early start high-dose, late start high-dose, and BIIB092 total). Listings will include all data in placebo-controlled and LTE period (all data in the study), with an indicator of the study period (pre-dosing, placebo-controlled, or LTE) for each record when the event occurred.

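### No adverse-event table in the LTE SAP computes the stated primary LTE endpoint, and the treatment-emergence rule contradicts the active-treatment tables used in its place

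*SAP*

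**What the plan says.** Protocol Section 6 gives the primary LTE endpoint as "Incidence of AEs and SAEs over the placebo-controlled period and long-term extension (LTE) period of the study", and SAP 2.1 repeats it: "incidence of AEs and SAEs over the placebo-controlled period and LTE period of the study". Neither limits it to time on BIIB092 or leaves out a group.

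SAP 3.2 defines three analysis periods:

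- **Item 1, LTE period.** "Only data in the LTE period will be included", for participants dosed in the LTE. The item adds: "This LTE analysis period will be applied to all the AE analyses".
- **Item 2, placebo-controlled and LTE period.** "All the data in the placebo-controlled and LTE periods will be included in these analyses", for everyone dosed in the study, whether or not they entered the LTE. Its named uses are "including, but not limited to all efficacy analyses and listings".
- **Item 3, active treatment period.** Early starters (randomised to BIIB092) contribute both periods. Late starters (randomised to placebo, then switched) contribute LTE data only. It takes in all dosed participants "except for subjects who received only placebo in the placebo-controlled period and did not get dosed in the LTE period". An AE incidence rate is its worked example.

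SAP 5.4.2 then says that "for either analysis period in this SAP (LTE period or placebo-controlled and LTE active treatment period), AE data will be summarized" by LTE treatment group. The same section defines a treatment-emergent AE as one that begins or worsens after the first LTE infusion, and by default admits only such events to tables. SAP 5.4.2.1 gives the overview table for items 1 and 3, the AE incidence tables for item 1, and starred tables as incidence rates for item 3. SAP 5.4.2.2 starts follow-up for the active-treatment rates at the first BIIB092 dose, which for early starters lies in the placebo-controlled period.

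**The concern.** A primary endpoint should have one definition and a table that computes it. Here the only period whose scope matches the endpoint (item 2) is used for AEs in listings alone. A report could present the LTE-period figure, the active-treatment figure or the endpoint as worded, and call any of them the primary result. They differ in who is counted and when counting starts.

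The substitute also conflicts with itself. Item 1 claims all AE analyses for the LTE-only period, while item 3 and SAP 5.4.2.1 place some of them on active treatment. The treatment-emergence rule makes this worse. If it is programmed as written, the tables meant to show cumulative BIIB092 exposure would omit what happened to early starters during the placebo-controlled period.

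**Working it through.** The plan gives no figure to reproduce, so the check sets the sections side by side and follows the rules through.

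**1. What each output counts**

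| Output | Early starters' events before the LTE | Late starters' events on placebo | Placebo-only participants |
|---|---|---|---|
| Endpoint as stated (Protocol 6, SAP 2.1) | yes | yes | yes |
| LTE-period incidence tables (SAP 5.4.2.1) | no | no | no |
| Active-treatment tables, by SAP 3.2 item 3 | yes | no | no |
| Active-treatment tables, with the SAP 5.4.2 emergence rule | no, unless worsened in the LTE | no | no |
| AE listings (SAP 5.4.2) | yes | yes | yes |

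No table row matches the first row. The open-ended wording of item 2 does not admit AE tables, because SAP 5.4.2 names only the other two periods for AE summaries.

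**2. The emergence rule against the rest of the plan.** Protocol 16.3.2.1 dates treatment emergence from first dosing. SAP 3.4 sets Study Day 1 of the active treatment period at the first BIIB092 dose. SAP 5.4.2 sets it at the first LTE infusion for all groups. An early starter who never entered the LTE belongs to the active treatment period by item 3, yet has no LTE infusion from which to date an event.

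**3. Effect on the active-treatment rates.** Inputs: the LTE starts at Week 80 and the last scheduled visit is Week 238 (Protocol 7.2). Let L be an early starter's follow-up in weeks from the first LTE dose. Read literally, events are counted over L weeks and follow-up over 80 + L weeks. For rare events at a constant rate,

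reported rate / consistent rate = L / (80 + L).

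- L = 24: 24/104 = 0.23.
- L = 158 (238 − 80, the scheduled maximum): 158/238 = 0.66.

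For a late starter the ratio is L/L = 1. At equal underlying rates and L = 24, the early-start rate would look about 104/24 = 4.3 times lower than the late-start rate. SAP 5.4.2.2 introduces these rates precisely because the two high-dose groups have active periods of different length.

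L = 24 is an assumption. The combined exposure categories in SAP 5.2.4 end at 26 infusions, against 20 planned in the placebo-controlled period (Protocol 11.1.1): 26 − 20 = 6 infusions, or 6 × 4 = 24 weeks. SAP 5.6.2 says that no participant reached Week 226, so actual follow-up was below the scheduled maximum.

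**4. Follow-up in the endpoint but outside every AE table.** For a late starter this is 80/(80 + L): 80/104 = 77% at L = 24 and 80/238 = 34% at L = 158. By planned allocation the placebo arm is 176/528, one third of participants. The arm split of the 654 actually randomised is not given.

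**The case against.** The strongest reply is that the SAP made a sensible choice. The objective is the safety of BIIB092, and events on placebo do not inform it. Item 3 states the rule openly, and Protocol 16.1 already separates the two periods. A separate SAP covers the placebo-controlled period, and the combined AE listing spans the whole study. LTE safety is descriptive, with no test or decision rule attached. All of this stands, and it limits the weight of the point. It does not give the stated endpoint a table.

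Item 1 can be read charitably as saying only that every listed AE table is produced for the LTE period. The emergence rule may likewise have been meant for those tables, since the companion definition of a pre-treatment AE refers to the LTE period. But no second rule is supplied for the active-treatment tables, so a programmer has only the LTE anchor to apply.

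Three stronger readings are tempting and not supported:

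- A reader might infer that safety data are lost or hidden. The listings retain them, and the placebo-controlled SAP, which is not among the documents, may tabulate them.
- A reader might count the placebo-only participants by applying the 20% dropout in Protocol 16.10. That figure is a Week 78 assumption for CDR-SB power. LTE entry is elective (Protocol 11.5), and non-entry among placebo participants is not given.
- A reader might assume AE percentages and a constant hazard to show how far the reported incidences would differ. The documents give no AE rates on which to base that.

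**Conclusion.** The point holds as a mismatch between endpoint and analysis, with contradictory rules for the substitute. No AE or serious-AE table in the LTE SAP computes the primary LTE endpoint. The active-treatment tables that come closest omit late starters' placebo phase and placebo-only participants by design. With the emergence rule as written, they also omit about 80 weeks of early starters' on-BIIB092 events while the rate denominator keeps that time.

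The first part is certain from the text. The second depends on the emergence rule being programmed literally. The rate ratios of 0.23 to 0.66 further assume rare events, a constant rate and the stated LTE follow-up; they show the mechanism and are not predictions. The number of participants affected cannot be derived from the documents. This should be corrected before tables are run. It does not make an on-BIIB092 safety summary inappropriate.

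**What to change.** 1. **Give the endpoint one definition.** State in SAP 2.1, and in Protocol Section 6 at its next amendment, that the primary LTE endpoint is the incidence of AEs and serious AEs from the first BIIB092 dose (SAP 3.2 item 3), with LTE-period incidence as a second summary. The overview table in SAP 5.4.2.1 already covers both periods. Alternatively, keep the endpoint and add one overall AE and serious-AE table on SAP 3.2 item 2, showing late starters' placebo-phase events separately so that they are not read as events on BIIB092.
2. **Narrow SAP 3.2 item 1** so that its sentence on AE analyses refers only to the LTE-period tables.
3. **Correct the treatment-emergence rule in SAP 5.4.2** by tying it to Study Day 1 of each analysis period as set in SAP 3.4. Active-treatment tables then count early starters' events from their first BIIB092 dose, matching the SAP 5.4.2.2 denominator. Without this step the restated endpoint would still not be computed.
4. **Keep the combined AE listing** in SAP 5.4.2.

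Cost: SAP wording, a treatment-emergence flag for each analysis period, and at most one extra table. No new data are needed. The drawback of restating the endpoint is that it changes the wording of a primary endpoint. If made in the protocol it needs an amendment, which goes to the ethics committee under Protocol 19.3; the extra-table route avoids that.

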2.2 Exploratory LTE Objectives and Endpoints

- To further evaluate the immunogenicity of BIIB092 after multiple doses in participants with MCI due to AD or with mild AD as measured by the incidence of anti-BIIB092 antibodies in serum over time up to Week 238.
- To further assess the effect of BIIB092 on disease progression as measured by fluid and radiological biomarkers, as well as additional clinical and health outcomes as measured by the following:
 - Changes over the placebo-controlled period and LTE period on the CDR-SB, MMSE, ISLT, Category Fluency and Letter Fluency tests from the DKEFS, DSST, Trails A, eCog, ADCS-ADL, FAQ, ADAS-Cog-13 (13-item), and NPI-10
 - Changes over the placebo-controlled period and LTE period on the ZBI, QoL-AD, and RUD-Lite
 - Changes over the placebo-controlled period and LTE period in CSF and blood biomarkers (for those who consent to participate in the optional CSF sampling substudy)
 - Changes over the placebo-controlled period and LTE period on 18F-MK6240 PET and MRI brain morphometric measures (for those who consent to participate in the optional PET substudy)
- To assess BIIB092 PK in serum (trough serum BIIB092 concentrations) and in CSF (for those who consent to participate in the optional CSF sampling substudy) from the samples collected at the visits indicated in the Schedule of Activities in participants with MCI due to AD or with mild AD.

2.3 Study Design

This is a Phase 2, randomized, double-blind, placebo-controlled, parallel-group study consisting of a double-blind, placebo-controlled period and an LTE period.

The study includes 2 substudies to address exploratory study objectives: a tau PET substudy and a CSF sampling substudy. The tau PET substudy is mandatory at study sites that have access to the ¹⁸F-MK6240 PET radioligand and have the capability to perform ¹⁸F-MK6240 PET scans. During the placebo-controlled period, the CSF sampling substudy is mandatory at all study sites that do not have access to the ¹⁸F-MK6240 PET radioligand. Participants will provide consent during Screening to participate in at least 1 of these substudies during the placebo-controlled period. Participants enrolled in the LTE period and who are participating in the tau PET substudy are required to continue participation in the tau PET substudy. Participation in the CSF sampling substudy during the LTE will be optional for all study participants, although participation is encouraged.

This study will be conducted in participants aged 50 to 80 years, inclusive, with MCI due to AD or mild AD according to National Institute on Aging-Alzheimer's Association criteria. Participants must have amyloid beta positivity confirmed at Screening by either CSF sampling or an amyloid PET scan. Participants must also perform at least 1 standard deviation below the age-adjusted normative mean on either the ISLT or the International Shopping List Test Delayed Recall and have a CDR global score of 0.5 for MCI due to AD or 0.5 or 1 for mild AD, an MMSE score of 22 to 30 (inclusive), and a CDR Memory Box score of ≥ 0.5 .

During the dose-blinded LTE period, participants will receive BIIB092 by IV once every 4 weeks beginning at Week 80. Participants who were randomized to receive BIIB092 during the placebo-controlled period will continue to receive BIIB092 at the dose they were randomly assigned. Participants randomized to receive placebo during the placebo-controlled period will receive BIIB092 at the high dose (2000 mg) once every 4 weeks during the LTE period.

The total duration for participants who complete the placebo-controlled period and do not enter the LTE period will be approximately 99 weeks. For participants who complete both the placebo-controlled period and the LTE period, the total study duration will be approximately 247 weeks.

Participants who meet the LTE inclusion and exclusion criteria will be eligible to enter the dose-blinded LTE period, which includes the LTE Screening Period of approximately 4 weeks starting at Week 76, the 144-week Treatment Period starting at Week 80, the EOS Visit at Week 226, and the Follow-up Visit at Week 238.

Participants will have approximately 39 outpatient clinic visits during the LTE period:

[figure not shown]
- Participant eligibility will be determined at Week 76 or Week 78 of the placebo-controlled period and confirmed at Week 80 of the LTE period.
- At the Week 80 Visit, eligible participants will have scheduled assessments per the Schedule of Activities and receive the first infusion of BIIB092 during the LTE period. All participants receiving placebo in the placebo-controlled period will receive BIIB092 at the high dose (2000 mg) once every 4 weeks during the LTE period.
- Participants will return to the clinic at 4-week intervals during the Treatment Period for infusions of study treatment and study assessments.

- The last dose of study treatment will be administered at Week 224 (End-of-Treatment Visit). The EOS Visit will occur at Week 226 and the Follow-up Visit at Week 238.
 - Participants who discontinue study treatment prematurely will be asked to remain in the study and continue all protocol-specified visits and procedures. These participants should be encouraged to attend at least the Week 104, 128, 152, 176, 200, and 226 Visits, depending on when treatment was discontinued, and undergo all the scheduled procedures. At a minimum, these visits should include assessment of AEs/SAEs and concomitant medications and key clinical assessments, including at least the CDR, MMSE, ISLT, ADAS-Cog 13, ADCS-ADL, and FAQ. Participants who discontinue study treatment prematurely will also be asked to return to the study site for a Follow-up Safety Visit 14 weeks after receiving the last dose of study treatment.
 - Participants who withdraw from the study prematurely are to return to the study site for an Early Termination Visit and assessments and for the Follow-up Safety Visit 14 weeks after receiving the last dose of study treatment.

Certain visits during the study may be conducted as home visits as specified in the Schedule of Activities, if the Investigator is in agreement and appropriate services are available to perform the required study procedures and adequately monitor for potential safety events.

2.4 Study Schematic

Figure 1: Study Design

Aβ = amyloid beta; AD = Alzheimer's disease; EOS = End of Study; LTE = long-term extension; MCI = mild cognitive impairment; N = number of participants; Q4W = once every 4 weeks; Q12W = once every 12 weeks

Note: Overall, participants will have a 2:1 chance of being randomized to BIIB092 versus placebo during the placebo-controlled period, and all participants will receive BIIB092 during the dose-blinded LTE period.

Note: The study comprises a double-blind, placebo-controlled period and an LTE period. The total duration for participants who complete the placebo-controlled period and do not enter the LTE period will be approximately 99 weeks. The total study duration for participants who complete both the placebo-controlled period and the LTE period will be approximately 247 weeks. The double-blind placebo-controlled period comprises a Screening Period of approximately 9 weeks (65 days), a Treatment Period of 76 weeks, and for participants not entering the LTE period, an EOS Visit at Week 78 and a Follow-up Safety Visit at Week 90, or approximately 14 weeks after the last dose of study treatment. The LTE period comprises an LTE Screening Period of approximately 4 weeks starting at Week 76, a 144-week Treatment Period starting at Week 80, an

CONFIDENTIAL

The information contained herein may not be used, disclosed, or published without the written consent of Biogen MA Inc.

	Statistical Analysis Plan Long-Term Extension Period	V1.0
---	--	-------------

EOS Visit at Week 226, and a Follow-up Safety Visit at Week 238, or approximately 14 weeks after the last dose of study treatment.

CONFIDENTIAL

The information contained herein may not be used, disclosed, or published without the written consent of Biogen MA Inc.

3 Definitions

3.1 Analysis Sets

- **Full Analysis Set (FAS):**
The FAS includes all randomized subjects who received at least one dose of study treatment (BIIB092 or placebo). In analyses performed on the FAS, subjects will be analyzed, based on the intention-to-treat principle, according to their randomized treatment assignment regardless of treatment received.
- **Safety Analysis Set:**
The safety Analysis Set includes all randomized subjects who received at least one dose of study treatment (BIIB092 or placebo), essentially the same set of participants included in the FAS. In analyses performed on the Safety Analysis Set, subjects will be analyzed according to their actual treatment received.
- **Safety MRI Evaluable Set:**
The Safety MRI Evaluable Set is defined as subjects in the FAS who had at least one post-baseline safety MRI scan.
- **Serum PK Evaluable Set:**
The serum PK evaluable set is defined as subjects in the FAS who had at least one measurable post-baseline BIIB092 concentration in serum before the End of Study of LTE.
- **CSF PK Evaluable Set:**
The CSF PK evaluable set is defined as subjects in the FAS who had at least one measurable post-baseline BIIB092 concentration in CSF.
- **CSF PD Evaluable Set:**
The CSF PD evaluable set is defined as subjects in the FAS who had lumbar puncture (LP), which will be used in analyses, such as subject accounting and summary of AE related to LP. The CSF PD Modified Evaluable Set is defined as subjects in the FAS who have baseline and at least one post baseline assessment of the specific parameter being analyzed in CSF.
- **Tau PET Evaluable Set**
The tau PET evaluable set is defined as subjects in the FAS who had tau PET, which will be used in analyses, such as subject accounting and summary of AE related to tau PET. The tau PET Modified Evaluable Set is defined as subjects in the FAS who had a valid baseline and a post-baseline tau PET SUVR measure using the 18F-MK6240 tracer.

	Statistical Analysis Plan Long-Term Extension Period	V1.0
---	---	-------------

- Anti-drug antibody (ADA) Evaluable Set:
The evaluable set for anti-drug antibody is defined as subjects in the FAS who have an evaluable post-baseline ADA sample.

